## 2.5 Rationale for choice of comparators drugs

Not applicable.

## 3 Objectives and endpoints

Objectives and related endpoints are described in Table 3-1 below.

**Table 3-1 Objectives and related endpoints**

Objective	Endpoint	Analysis
Primary To collect and assess long term safety of everolimus	Frequency and nature of AEs	Refer to Section 10.4

## 4 Study design

### 4.1 Description of study design

This is a multi-center, open label study to collect and assess long-term safety of everolimus in patients currently being treated in a Novartis-sponsored Oncology CD & MA study, who are not progressing on the current study treatment as defined by the parent protocol and are unable to access everolimus treatment outside of a clinical study. Parent studies eligible to participate in the roll-over study will be decided by Novartis. Investigator initiated trials (IITs) will not be included.

There will be no screening period for this study. Eligible patients can start their treatment with everolimus as soon as they enter the study. All patients must report to the study site for their first visit and commence study participation. Patients must return to the study center at least on a yearly basis ( $\pm$  3 months) for resupply of study medication. Limited drug dispensing information will be collected. The patient may return to the clinic at any given time as per standard of care or be treated by physician's recommendation, however at least one study visit every year will be scheduled and AEs reported at general medical care will be collected continuously throughout the study. When AEs are observed, additional visits will be arranged by investigator's discretion (see [Section 6.3.2](#)).

Patients entering the roll-over protocol should be followed at the investigator's discretion for known or clinically notable AEs that occur on everolimus treatment as described in the current version of the everolimus IB.

[figure not shown]
Patients will continue to be treated in the roll-over protocol until they are no longer benefiting from their everolimus treatment as defined in the parent protocol (disease progression), they develop unacceptable toxicities, they withdraw consent, they are non-compliant to the protocol,

the investigator feels it is no longer in the patient's best interest to continue everolimus therapy or the patient dies, whichever comes first.

A patient will reach the end of study when everolimus treatment is permanently discontinued.

The study is expected to remain open for 5 years or until such time that enrolled patients no longer need treatment with everolimus, whichever comes first.

**Figure 4-1 Study design**

## 4.2 Timing of interim analyses and design adaptations

Not applicable.

## 4.3 Definition of end of the study

The end of the study is defined as when the patient permanently discontinues treatment with everolimus and the end of treatment visit has been performed for each patient.

## 4.4 Early study termination

The study is expected to remain open for 5 years or until such time that enrolled patients no longer need treatment with everolimus, whichever comes first.

The study can be terminated at any time for any reason by Novartis. Should this be necessary, the patient should be informed as soon as possible and should stop taking study labeled drug. Assessments should be performed as described in [Section 7.1.4](#) for a prematurely withdrawn patient. The investigator may be informed of additional procedures to be followed in order to ensure that adequate consideration is given to the protection of the patient's interests. The investigator will be responsible for informing IRBs and/or ECs of the early termination of the trial.

## 5 Population

### 5.1 Patient population

The investigator or designee must ensure that only patients who meet all the following inclusion and none of the exclusion criteria are offered treatment in the study.

### 5.2 Inclusion criteria

Patients eligible for inclusion in this study have to meet **all** of the following criteria:

1. Patient is currently enrolled in a Novartis-sponsored study, receiving everolimus and has fulfilled all their requirements in the parent study.
2. Patient is currently benefiting from the treatment with everolimus, as determined by the guidelines of the parent protocol.
3. Patient has demonstrated compliance, as assessed by the investigator, with the parent study protocol requirements.
4. Willingness and ability to comply with scheduled visits and treatment plans.
5. Written informed consent obtained prior to enrolling into the roll-over study.
  - If consent cannot be expressed in writing, it must be formally documented and witnessed, ideally via an independent trusted witness.

### **5.3 Exclusion criteria**

Patients eligible for this study must not meet **any** of the following criteria:

1. Patient has been permanently discontinued from everolimus study treatment in the parent study.
2. Sexually active males, unless they use a condom during intercourse while taking drug and for 8 weeks after stopping study medication. Males also should not father a child in this period. A condom is required to be used also by vasectomized men in order to prevent delivery of the drug via seminal fluid.
3. Pregnant or nursing (lactating) women, where pregnancy is defined as the state of a female after conception and until the termination of gestation, confirmed by a positive hCG laboratory test.
4. Women of child-bearing potential, defined as all women physiologically capable of becoming pregnant, unless they are using highly effective methods of contraception during dosing and for 8 weeks after everolimus last dose. Women are considered post-menopausal and not of child-bearing potential if they have had 12 months of natural (spontaneous) amenorrhea with an appropriate clinical profile (e.g. age appropriate, history of vasomotor symptoms) or have had surgical bilateral oophorectomy (with or without hysterectomy) or tubal ligation at least six weeks prior to randomization. In the case of oophorectomy alone, only when the reproductive status of the woman has been confirmed by follow up hormone level assessment is she considered not of child-bearing potential

Highly effective contraception methods include:

- Total abstinence (when this is in line with the preferred and usual lifestyle of the subject. Periodic abstinence (e.g., calendar, ovulation, symptothermal, post-ovulation methods) and withdrawal are not acceptable methods of contraception)
- Female sterilization (have had surgical bilateral oophorectomy with or without hysterectomy) or tubal ligation at least six weeks before taking study treatment. In case of oophorectomy alone, only when the reproductive status of the woman has been confirmed by follow up hormone level assessment
- Male sterilization (at least 6 months prior to screening). For female subjects on the study the vasectomized male partner should be the sole partner for that subject.

- Use of oral, injected or implanted hormonal methods of contraception or placement of an intrauterine device (IUD) or intrauterine system (IUS), or other forms of hormonal contraception that have comparable efficacy (failure rate <1%), for example hormone vaginal ring or transdermal hormone contraception.
- In case of use of oral contraception women should have been stable on the same pill for a minimum of 3 months before taking study treatment.

If a study patient or partner becomes pregnant or suspects being pregnant during the study or within 30 days after the last dose of everolimus, the investigator needs to be informed immediately and ongoing study treatment with everolimus has to be stopped immediately.

## 6 Treatment

### 6.1 Study treatment

For study treatment refer to everolimus plus combination drugs used in the parent study and for investigational treatment refer to everolimus.

#### 6.1.1 Dosing regimen

**Table 6-1 Dose and treatment schedule**

Investigational treatments	Pharmaceutical form and route of administration	Dose	Frequency and/or Regimen
RAD001/everolimus	Tablet for oral use	2.5 – 10 mg/day	Daily

Everolimus will be provided as 2.5 mg or 5 mg tablets. The investigational treatment is to be stored in a secure locked area while under the responsibility of the investigator. The investigator should assess compliance of study drug at each patient visit (see [Section 6.6.3.1](#)). Receipt and dispensing of investigational drug must be recorded by an authorized person at the investigator's site (see [Section 6.6.3.2](#)).

At the time of transition to the roll-over study, the starting dose of everolimus should be the same as the last dose that was given in the parent study. Dose modification thereafter may be done at the discretion of the investigator based upon what is in the patient's best interest.

Patients will be instructed to take everolimus orally with a glass of water, once daily at the same time each day, either consistently with food or consistently without food. Dietary habits at the time of enrolling in the study from the parent study should be kept as consistent as possible throughout the study. The tablet should be swallowed as a whole and should not be chewed or crushed.

Please refer to the current everolimus IB and [Section 6.3](#) for further important information on potential dosing precautions regarding concomitant medication interaction with cytochrome p450, p-glycoprotein, and CYP3A4 and the recommended dosing guidance.

#### 6.1.2 Ancillary treatments

Not applicable.

### **6.1.3     Rescue medication**

Not applicable.

### **6.1.4     Guidelines for continuation of treatment**

Please refer to the [Section 6.3.1](#).

### **6.1.5     Treatment duration**

Patients will continue to be treated in the roll-over protocol until they are no longer benefiting from their everolimus treatment as defined in the parent protocol (disease progression), they develop unacceptable toxicities, they withdraw consent, they are non-compliant to the protocol, the investigator feels it is no longer in the patient's best interest to continue everolimus therapy or the patient dies, whichever comes first. A patient will reach the end of the roll-over study when everolimus treatment is permanently discontinued.

The study is expected to remain open for 5 years or until such time that enrolled patients no longer need treatment with everolimus, whichever comes first.

### **6.1.6     Other study treatment**

Please refer to the parent protocol and Package Insert for treatment, management of toxicities and dose modifications.

## **6.2       Dose escalation guidelines**

Not applicable.

## **6.3       Dose modifications**

### **6.3.1     Dose modifications and dose delay**

Patients will begin the roll-over study at the same dose as the last dose administered in the parent protocol. Dose adjustments are permitted to allow the patient to continue the study treatment at the investigator's discretion. The same dose modifications as followed in the parent protocol may apply at the investigator's discretion, but the dose of everolimus will not be over 10 mg/day.

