### **6.4.2 Permitted concomitant therapy requiring caution and/or action**

Everolimus is metabolized by CYP3A4 in the liver and to some extent in the intestinal wall. Therefore, the following are recommended:

- Co-administration with strong inhibitors of CYP3A4 (e.g., ketoconazole, itraconazole, ritonavir) or P-glycoprotein (PgP) inhibitor should be avoided.
- Co-administration with moderate CYP3A4 inhibitors (e.g., erythromycin, fluconazole) or PgP inhibitors should be used with caution. If a patient requires co-administration of moderate CYP3A4 inhibitors or PgP inhibitors, reduce the dose of study drug to half the currently used dose. Additional dose reductions to every other day may be required to manage toxicities. If the inhibitor is discontinued, the study drug dose should be returned to the dose used prior to initiation of the moderate CYP3A4/PgP inhibitor.
- Seville orange, star fruit, grapefruit and their juices affect P450 and PgP activity. Concomitant use should be avoided.
- Co-administration with strong inducers of CYP3A4 should be avoided. If a patient requires co-administration of strong CYP3A4 inducers (i.e., phenytoin, carbamazepine, rifampin, rifabutin, phenobarbital, St. John's wort), an increase in the dose of study drug up to twice the currently used daily dose should be considered, 5mg increments. Enzyme induction usually occurs within 7-10 days; therefore study drug dose should be increased by one increment 7 days after the start of the inducer therapy. If no safety concerns are seen within the next 7 days, the dose can be increased again one additional increment up to a maximum of twice the daily dose used prior to initiation of the strong CYP3A4 inducer.
- This dose adjustment of study drug is intended to achieve similar AUC to the range observed without inducers. However, there are no clinical data with this dose adjustment in patients receiving strong CYP3A4 inducers. If the strong inducer is discontinued the study drug dose should be returned to the dose used prior to initiation of the strong CYP3A4/PgP inducer.

Please refer to [Table 6-2](#) listing relevant inducers and inhibitors of CYP3A and to [Table 6-3](#) for a list of relevant substrates, inducers, and inhibitors of PgP. Please refer to the most recent Investigator's Brochure for a complete list.

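### Above 5 mg/day the 10 mg/day limit and the twice-dose limit with a strong inducer conflict, and rifampin and St John's wort fall under two opposite dose adjustments; the protocol does not say which governs

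*Protocol*

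**What the plan says.** **Upper limit.** Protocol Section 6.3.1 starts each patient on the last parent-study dose and allows changes at the investigator's discretion, "but the dose of everolimus will not be over 10 mg/day". The protocol summary and Table 6-1 (Section 6.1.1) both give 2.5 to 10 mg/day. Tablets are 2.5 mg and 5 mg and are to be swallowed whole.

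**Strong CYP3A4 inducers (Section 6.4.2).** "Co-administration with strong inducers of CYP3A4 should be avoided". If one is required, "an increase in the dose of study drug up to twice the currently used daily dose should be considered, 5mg increments". The first step comes 7 days after the inducer is started. If no safety concern appears in the following 7 days, "the dose can be increased again one additional increment up to a maximum of twice the daily dose used prior to initiation". Six agents are named, including rifampin and St John's wort. The 10 mg/day figure does not appear.

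**PgP inhibitors (Section 6.4.2).** One bullet pairs strong CYP3A4 inhibitors with PgP inhibitors: "or P-glycoprotein (PgP) inhibitor should be avoided". The next bullet allows moderate CYP3A4 inhibitors or PgP inhibitors with caution. If one is required, the instruction is to "reduce the dose of study drug to half the currently used dose". The reader is sent to Table 6-3 "for a list of relevant substrates, inducers, and inhibitors of PgP".

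**Tables.** Table 6-2 lists rifampin and St John's wort as strong inducers. Table 6-3 gives them as its only two inducers and lists both again in its row of PgP and dual PgP/CYP3A inhibitors.

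**The concern.** There are two separate conflicts.

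1. *Maxima.* A patient above 5 mg/day who needs a strong inducer has two written upper limits, and the twice-dose limit is the higher. A site that uses the Section 6.4.2 increase leaves the range in the summary and Table 6-1. It also breaks the Section 6.3.1 limit if that clause covers interaction dosing.
2. *Direction.* For rifampin and St John's wort, Section 6.4.2 read with Table 6-3 supports both an increase and a halving.

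The only endpoint is the frequency and nature of adverse events (Table 3-1). Two sites could dose similar patients differently, even in opposite directions, while each follows a written instruction. Section 6.4.2 itself acknowledges that the inducer adjustment has no clinical data behind it. Section 12 allows no authorized deviations, so a site cannot settle the conflict by asking the sponsor to approve one.

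**Working it through.** **Inputs.** Limit 10 mg/day (Section 6.3.1; upper end of the range in the summary and Table 6-1). Tablets 2.5 and 5 mg (Section 6.1.1). Step 5 mg, maximum twice the prior dose (Section 6.4.2, inducer bullet). Halving (Section 6.4.2, inhibitor bullet). Whole tablets make four daily doses within the range: 2.5, 5, 7.5 and 10 mg.

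**Step 1: when does a 5 mg step fit both limits?** Let d be the current daily dose.
- Twice-dose limit: d + 5 ≤ 2d, so d ≥ 5.
- 10 mg limit: d + 5 ≤ 10, so d ≤ 5.
- Both hold only at d = 5, which is one of the four doses.

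**Step 2: each dose in turn (mg/day).**

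| d | 2d | 5 mg steps within 2d | Highest step relative to 10 mg | Half dose |
|---|---|---|---|---|
| 2.5 | 5 | none (2.5 + 5 = 7.5, above 5) | – | 1.25 |
| 5 | 10 | 10 | 1.0 | 2.5 |
| 7.5 | 15 | 12.5 (next step 17.5, above 15) | 1.25 | 3.75 |
| 10 | 20 | 15, then 20 | 2.0 (first step 1.5) | 5 |

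At 7.5 and 10 mg the first step already passes 10 mg/day. At 2.5 mg the two maxima also differ (5 against 10), but twice the dose stays inside the range. The difficulty there is that one step overshoots Section 6.4.2's own maximum.

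**Step 3: double listing.** Rifampin and St John's wort are 2 of the 8 strong inducers in Table 6-2, 2 of the 6 named in Section 6.4.2, and 2 of the 2 in the inducer row of Table 6-3. Both are also in that table's inhibitor row. Six moderate or weak inducers in Table 6-2 (ritonavir, tipranavir, amprenavir, aprepitant, ginkgo, telaprevir) also appear in an inhibitor row. Section 6.4.2 gives a dose increase only for strong inducers, so those six carry no opposing instruction and are not counted.

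**Step 4: gap between the two readings for these two agents.** Ratio = highest dose under the inducer bullet ÷ halved dose.

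| d | 5 mg steps, no 10 mg limit | 5 mg steps, 10 mg limit applied |
|---|---|---|
| 2.5 | 2.5/1.25 = 2.0 | 2.0 |
| 5 | 10/2.5 = 4.0 | 4.0 |
| 7.5 | 12.5/3.75 = 3.3 | 7.5/3.75 = 2.0 |
| 10 | 20/5 = 4.0 | 10/5 = 2.0 |

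If the step size is ignored and exactly twice the dose is used, the ratio is 2d ÷ (d/2) = 4.0 at every dose. With the 10 mg limit it is then 4.0, 4.0, 10/3.75 = 2.7 and 2.0. If no increase is made, it is d ÷ (d/2) = 2.0 throughout.

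**Step 5: tablets (secondary).** Half of 2.5 mg is 1.25 mg, below the stated range. Neither 1.25 mg nor 3.75 mg can be made up daily from whole 2.5 or 5 mg tablets.

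**The case against.** **The maxima can both be met.** Section 6.3.1 is categorical, whereas the inducer increase is something to consider, up to a ceiling. A site that never exceeds 10 mg breaks neither. Section 6.1.1 also sends the reader to Section 6.3, where the 10 mg clause sits, for interaction dosing. This stands as a limit on the finding. But at 10 mg/day it leaves no increase at all, and the protocol does not say that is intended. The 10 mg clause can also be read as covering only modifications carried over from the parent protocol. On that reading the summary and Table 6-1 would still be exceeded.

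**The inducer reading is the more natural one.** The inducer bullet names both agents, and the halving bullet names neither. The wording on stopping the inducer, "the study drug dose should be returned to the dose used prior to initiation of the strong CYP3A4/PgP inducer", covers PgP inducers. The pharmacokinetics text in Section 1.2.1.2 says rifampin lowers everolimus levels. Table 6-3 is a reference list with no dose instruction of its own. All of this stands as evidence of likely intent. However, the pharmacokinetics text does not mention St John's wort, Section 6.4.2 directs readers to Table 6-3 to identify PgP inhibitors, and no order of precedence is given.

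**The consequence may be small.** The study is descriptive, doses are already at the investigator's discretion, dose changes are recorded (Section 6.6), and both classes are to be avoided. No effect on adverse event rates has been shown. That is fair, and it limits the severity. Discretion does not, however, reconcile a stated range with a dosing paragraph that exceeds it.

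**The Investigator's Brochure may settle it.** Sections 6.1.1 and 6.4.2 both refer to it, and it was not available for this review.

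**Conclusion.** The concern holds. Above 5 mg/day the protocol gives two maxima that cannot both be used in full. The Section 6.4.2 steps reach 12.5 mg from 7.5 mg and 20 mg from 10 mg, which is 1.25 and 2.0 times the 10 mg/day figure. Rifampin and St John's wort fall under opposite instructions. The gap is fourfold at 5 mg/day even with the 10 mg limit applied, and two- to fourfold at the other doses depending on the reading.

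The conflict arises only when co-administration cannot be avoided. The ratios assume whole-tablet daily doses and the readings shown, and the one-in-four count in Step 1 is over possible doses, not patients. The documents give neither a dose distribution nor a frequency of use for these agents, so the number of patients affected is unknown. Confidence is high that the wording conflicts; whether the Investigator's Brochure resolves it cannot be judged here. This is a should-fix matter of internal consistency. It bears on patient safety and on the only endpoint.

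**What to change.** The sponsor should reconcile the protocol summary, Table 6-1 and Section 6.1.1, Section 6.3.1, Section 6.4.2, and Tables 6-2 and 6-3, so that the protocol:

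- states which maximum governs when a strong inducer is required;
- gives a single instruction for agents listed both as inducer and as PgP inhibitor;
- makes the increment, halving, dose-range and tablet-strength statements consistent with one another.

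Which statement is right is a clinical decision for the sponsor; no dose or rule is proposed here.

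The cost is one written amendment with the approvals in Section 12.1 (sponsor, ethics bodies, and Health Authorities where required). It adds no patients, visits or procedures.

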### **6.3.2     Follow-up for toxicities**

Patients whose treatment is interrupted or permanently discontinued due to an AE or clinically significant laboratory value, should be followed up at least once a week (or more frequently if clinically indicated) for 4 weeks, and subsequently at approximately 4-week intervals, until resolution or stabilization of the event, whichever comes first.

Appropriate clinical experts such as ophthalmologist, endocrinologist, dermatologist, psychiatrists etc. should be consulted as deemed necessary. Patients must be followed serious AEs for 30 days after the last dose of everolimus.

### 6.3.2.1 Follow up on potential drug-induced liver injury (DILI) cases

Patients with transaminase increase combined with TBIL increase may be indicative of potential DILI, and should be considered as clinically important events.

The threshold for potential DILI may depend on the patient's baseline AST/ALT and TBIL value; patients meeting any of the following criteria will require further follow-up as outlined below:

- For patients with normal ALT and AST and TBIL value at baseline: AST or ALT  $> 3.0 \times$  ULN combined with TBIL  $> 2.0 \times$  ULN
- For patients with elevated AST or ALT or TBIL value at baseline: [AST or ALT  $> 2 \times$  baseline AND  $> 3.0 \times$  ULN] OR [AST or ALT  $> 8.0 \times$  ULN], combined with [TBIL  $> 2 \times$  baseline AND  $> 2.0 \times$  ULN]

Medical review needs to ensure that liver test elevations are not caused by cholestasis, defined as ALP elevation  $> 2.0 \times$  ULN with R value  $< 2$  in patients without bone metastasis, or elevation of ALP liver fraction in patients with bone metastasis.

Note: (The R value is calculated by dividing the ALT by the ALP, using multiples of the ULN for both values. It denotes whether the relative pattern of ALT and/or ALP elevation is due to cholestatic (R  $\leq 2$ ), hepatocellular (R  $\geq 5$ ), or mixed (R  $> 2$  and  $< 5$ ) liver injury).

In the absence of cholestasis, these patients should be immediately discontinued from study drug treatment, and repeat LFT testing as soon as possible, preferably within 48 hours from the awareness of the abnormal results. The evaluation should include laboratory tests, detailed history, physical assessment and the possibility of liver metastasis or new liver lesions, obstructions/compressions, etc.

1. Laboratory tests should include ALT, AST, albumin, creatine kinase, total bilirubin, direct and indirect bilirubin, GGT, prothrombin time (PT)/INR and alkaline phosphatase.
2. A detailed history, including relevant information, such as review of ethanol, concomitant medications, herbal remedies, supplement consumption, history of any pre-existing liver conditions or risk factors, should be collected.
3. Further testing for acute hepatitis A, B, C or E infection and liver imaging (e.g. biliary tract) may be warranted.
4. Obtain PK sample, as close as possible to last dose of study drug, if PK analysis is performed in the study.
5. Additional testing for other hepatotropic viral infection (CMV, EBV or HSV), autoimmune hepatitis or liver biopsy may be considered as clinically indicated or after consultation with specialist/hepatologist.

All cases confirmed on repeat testing meeting the laboratory criteria defined above, with no other alternative cause for LFT abnormalities identified should be considered as "medically significant", thus, met the definition of SAE ([Section 8.2.1](#)) and reported as SAE using the term "potential drug-induced liver injury". All events should be followed up with the outcome clearly documented.

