All AEs should be treated appropriately. If a concomitant medication or non-drug therapy is given, this action should be recorded on the AE eCRF.

Once an AE is detected, it should be followed until its resolution or until it is judged to be permanent, and assessment should be made at each visit (or more frequently, if necessary) of any changes in severity, the suspected relationship to the study treatment, the interventions required to treat it.

Progression of malignancy (including fatal outcomes), if documented by use of appropriate method [for example, as per Response evaluation Criteria in Solid Tumors (RECIST) criteria for solid tumors or as per Cheson's guidelines for hematological malignancies], should not be reported as a SAE.

AEs separate from the progression of malignancy (example, deep vein thrombosis at the time of progression or hemoptysis concurrent with finding of disease progression) will be reported as per usual guidelines used for such events with proper attribution regarding relatedness to the drug.

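### Section 6.3.2.1: the bone-metastasis branch of the cholestasis definition has no R condition, so a case the adjacent note calls hepatocellular can fall outside the recommended stop

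*Protocol*

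**What the plan says.** Protocol section 6.3.2.1 sets laboratory criteria for potential drug-induced liver injury (DILI). With normal baseline values these are AST or ALT above 3.0 × ULN together with total bilirubin above 2.0 × ULN. A causation step follows: "Medical review needs to ensure that liver test elevations are not caused by cholestasis". Cholestasis is then defined in two branches:

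- Without bone metastasis: ALP above 2.0 × ULN with R below 2.
- With bone metastasis: "or elevation of ALP liver fraction in patients with bone metastasis". No R value and no multiple of ULN is attached to the liver fraction.

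The next note explains R: "The R value is calculated by dividing the ALT by the ALP, using multiples of the ULN for both values". It continues: "It denotes whether the relative pattern of ALT and/or ALP elevation is due to cholestatic" (R up to 2), hepatocellular (R of 5 or more) or mixed (between 2 and 5) injury. The note is not limited to patients without bone metastasis.

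The action depends on the outcome of that step: "In the absence of cholestasis, these patients should be immediately discontinued from study drug treatment", with liver tests repeated as soon as possible, preferably within 48 hours. The SAE term for potential DILI is reserved for "All cases confirmed on repeat testing meeting the laboratory criteria defined above, with no other alternative cause for LFT abnormalities identified".

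**The concern.** A separate branch for bone metastasis makes sense. Bone ALP raises total ALP and so lowers R, which makes a low R untrustworthy as a sign of cholestasis in these patients. It gives no reason to set aside a high R: a case that reaches R ≥ 5 despite any added bone ALP points more strongly away from a cholestatic pattern.

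As written, the definition and the note can classify the same patient differently, and the section does not say which prevails. Where they differ, the definition leads to the less cautious action. What could be lost is the prompt stop, the early repeat test and, indirectly, the potential-DILI SAE term, which needs confirmation on repeat testing. Long-term safety is the study's only objective, and Amendment 01 was issued in part to provide this liver guidance.

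**Working it through.** The plan states no figure to reproduce. The check applies the rules of section 6.3.2.1 to assumed patients.

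**Inputs from section 6.3.2.1.** Trigger (normal baseline): ALT > 3.0 and bilirubin > 2.0. R = ALT ÷ total ALP, both as multiples of ULN. Cholestasis without bone metastasis: ALP > 2.0 and R < 2. Hepatocellular by the note: R ≥ 5.

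**Assumptions.** The patient values are illustrative. Bilirubin is 3 × ULN throughout, so every case meets the trigger. An elevated liver fraction is taken as above 1.0 × ULN; the protocol gives no figure.

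**Two readings of the bone-metastasis branch.** The sentence can be parsed in two ways:

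- Reading 1: the ALP > 2.0 condition belongs only to the branch without bone metastasis. With bone metastasis, a raised liver fraction suffices.
- Reading 2: ALP > 2.0 governs both branches. With bone metastasis, cholestasis needs total ALP > 2.0 and a raised liver fraction.

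**Results** (all values × ULN; 'stop' means not cholestasis, so the recommendation applies):

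| Case | ALT | Total ALP | Liver fraction | R | No bone metastasis | Bone metastasis, reading 1 | Bone metastasis, reading 2 |
|---|---|---|---|---|---|---|---|
| 1 | 10 | 1.8 | 1.1 | 10/1.8 = 5.6 | stop | cholestasis | stop |
| 2 | 10.5 | 2.1 | 1.3 | 10.5/2.1 = 5.0 | stop | cholestasis | cholestasis |
| 3 | 20 | 3.5 | 2.5 | 20/3.5 = 5.7 | stop | cholestasis | cholestasis |
| 4 | 20 | 3.5 | normal | 5.7 | stop | stop | stop |
| 5 | 10 | 3.0 | 1.1 | 10/3.0 = 3.3 | stop | cholestasis | cholestasis |
| 6 | 4 | 3.5 | 3.0 | 4/3.5 = 1.1 | cholestasis | cholestasis | cholestasis |

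Cases 1 to 3 are hepatocellular by the note. Without bone metastasis all three fall under the stop. With it, reading 1 exempts all three and reading 2 exempts cases 2 and 3. Case 3 remains exempt even if an elevated liver fraction is taken to mean above 2.0. Case 4 shows that a normal liver fraction leaves the stop in place.

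**Size of the conflict zone.** R ≥ 5 means ALT ≥ 5 × total ALP. Under reading 2, total ALP > 2 then gives ALT > 5 × 2 = 10. Under reading 1 no floor on total ALP applies, so lower-ALP cases such as case 1 also qualify.

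**Effect of excluding R ≥ 5 from cholestasis.** Under reading 1, cases 1 to 3 move to stop; under reading 2, cases 2 and 3 do. Cases 4 to 6 do not change. Nothing changes without bone metastasis, where cholestasis already needs R < 2.

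**The case against.** The strongest reply is that this is a medical judgement about cause and not an automatic gate. The reviewer is asked whether cholestasis caused the elevations, and the note beside the definition supplies R for that question. Someone looking at ALT 20 and R = 5.7 has the answer in the next lines. This stands as a limit on harm. It does not settle the text, because the review is directed to cholestasis as defined, and the definition gives the other answer.

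The route is also narrow. It needs bone metastasis, a met trigger, R ≥ 5 and a liver fraction that has been measured and is raised. The work-up list reads "Laboratory tests should include ALT, AST, albumin, creatine kinase, total bilirubin, direct and indirect bilirubin, GGT, prothrombin time (PT)/INR and alkaline phosphatase"; it names alkaline phosphatase but not the liver fraction. The list is not exclusive, but the exemption arises only once someone has obtained that further test. This stands.

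Other safeguards exist. Treatment ends for unacceptable toxicity or when the investigator judges that continuing is not in the patient's interest (sections 2.1, 4.1 and 6.1.5), and dose changes are at the investigator's discretion (section 6.3.1). All patients meeting the laboratory criteria require further follow-up, and that sentence precedes the cholestasis step, so loss of the repeat test is arguable. Section 8.1.1 adds: "Once an AE is detected, it should be followed until its resolution or until it is judged to be permanent". An event judged medically significant is an SAE in any case (section 8.2.1) and must be reported within 24 hours regardless of causality (section 8.2.2). These reduce the harm, but none of them restores the specific recommendation to stop at once.

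A reader might infer that a raised liver fraction alone always makes a bone-metastasis case cholestasis. The documents do not establish this, because reading 2 is grammatically open and takes case 1 out. Nor do they support a general claim that only high-ALT cases are affected. The ALT > 10 limit holds under reading 2; under reading 1 a limit would need an assumed ordering of the total-ALP and liver-fraction multiples, which the documents do not give.

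**Conclusion.** The concern holds in a limited form. In section 6.3.2.1 a DILI-trigger case with bone metastasis, R ≥ 5 and a raised ALP liver fraction can literally count as cholestasis, although the adjacent note calls it hepatocellular, and so fall outside the recommended immediate stop and prompt repeat tests. Under reading 2 this is confined to total ALP above 2 and ALT above 10 × ULN; under reading 1 lower-ALP cases are included. A conflict survives both readings.

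A reader might go further and infer that such patients will be left on drug, or that the safety results will be wrong. The documents support neither. Medical review and the general stopping rules may catch the case, the planned adverse event tables are descriptive, and no stated figure changes. The number affected cannot be estimated and may be zero: the section provides for bone metastasis, but the sponsor decides which parent studies feed in (section 2.1). The patient profiles are assumed. The priority is minor, and the case for acting is that the correction is cheap and removes a rule that literally gives the less safe action.

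**What to change.** Add one sentence to section 6.3.2.1: *A case with R ≥ 5 by the formula in the note (total ALP) is not classed as cholestasis, whether or not bone metastasis is present.* This uses only the R the protocol already defines and introduces no new threshold. It is conservative, because added bone ALP can only lower R.

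The cost is one sentence by amendment, with no new procedure, eCRF field or listing. The downside is possibly a few more treatment stops and potential-DILI SAE reports, in patients who are benefiting and have no access to everolimus outside a clinical study (sections 1.1 and 2.1).

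Naming the liver fraction in the test list would be a clarification only. A numeric cut-off for its elevation, and the handling of mixed cases such as case 5, are matters of preference for hepatic safety experts. None of these is part of this request.
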